#### *Secondary outcomes*

- Postpartum diabetes control of women with GDM was assessed through the postpartum 6th week information form that developed by the researchers on the basis of the literature.
- Postpartum characteristics of neonates were assessed through the neonate's information form that developed by the researchers on the basis of the literature.

The flowchart of this study is shown in Figure 1. The patients followed up in the perinatology clinic were assigned to groups through randomization (drawing lots by the clinic nurse). Data collector checked patients in the perinatology clinic daily. If there were more than one patient who met the inclusion criteria, it was determined which group to take with the lottery method. When there was only one woman with GDM in the clinic, it was determined which group to take with the lot but the next patient was taken directly to the opposite group. When two patients were in the same room, they were taken into the same group in order not to have any ethical problems. The women in the both group were administered the introductory information form, the HPLP-II, the CES-D and the SF-36 in the first assessment.

The education program and also usual care applied to the intervention group. The education program consisted of three 45-min sessions, which included a face-to-face lecture with the dissemination and presentation of written and visual materials. Also each participant in the intervention group was given the *Health-Promoting Lifestyle Booklet* and the *Diary of a Woman with GDM* card. The booklet features all of the health-promoting practices (self-monitoring of blood glucose, nutrition, physical activity, stress, sleeping, smoking, self-care and breastfeeding). The *Diary of a Woman with GDM* card features the daily program that women should follow (the hours for main meals and snacks, insulin hours, etc.). The education and counseling were maintained through follow-up via phone for intervention group.

The women in the control group which receiving only usual care were followed according to the institution's routine diabetes follow-up protocol (monitoring blood glucose levels as frequently as indicated by the doctor, and patients are referred to dietitian and to diabetes nurse). To assess the effectiveness of the educational program, the HPLP-II, CES-D and SF-36 were re-administered to the intervention group four weeks after the first assessment (second assessment). The HPLP-II, CES-D and SF-36 were re-administered to the both groups in the postpartum 6th week (third assessment).

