## **Aim**

The aim of the study was to examine the effects of the **HPLEP** on maternal and neonatal health.

Hypotheses of this study;

H1: The **HPLEP** is effective for women with GDM in their adoption of a healthy lifestyle.

H2: The **HPLEP** is effective in reducing the symptoms of depression in women with GDM.

H3: The **HPLEP** is effective in improving the quality of life of women with GDM.

H4: The **HPLEP** is effective in reducing postpartum neonatal complications.

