### **Data collection**

Data were collected by the first author (both control and intervention group). All data were collected with questionnaires conducted through face-to-face structured interviews with the data collector.

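### Neonatal outcomes (H4) and postpartum diabetes control rest, as written, on the mother's report at interview, so differential reporting can enter the group comparison

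*Combined protocol and SAP*

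**What the plan says.** Under Aim, the fourth of four hypotheses is that the programme "is effective in reducing postpartum neonatal complications". Two secondary outcomes are listed, each with a form as its only stated source:

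- Neonates: "Postpartum characteristics of neonates were assessed through the neonate's information form that developed by the researchers on the basis of the literature".
- Mothers: "Postpartum diabetes control of women with GDM was assessed through the postpartum 6th week information form that developed by the researchers", again with the literature given as its basis.

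The Data collection section states the mode for the whole study: "All data were collected with questionnaires conducted through face-to-face structured interviews with the data collector". It makes no exception for these two forms. The same section says that the first author collected the data in both groups.

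The intervention is described under the Secondary outcomes heading: "The education program consisted of three 45-min sessions", with a booklet and a diary card, and "The education and counseling were maintained through follow-up via phone for intervention group". The control group had usual care only.

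The Data analysis section tests neonatal characteristics with chi-square and Mann-Whitney tests, and diabetes control with Fisher's exact test.

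**The concern.** A neonatal complication, a birth weight or a postpartum glucose result would normally be on record somewhere. The plan does not name a record. It describes an interview, held by one person who worked with both groups and for whom no blinding is described.

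The intervention itself could change reporting. Educated women may recognise and name a problem or a test result more readily. They may also give more favourable answers to an investigator they know. Error that is equal in both groups would mostly dilute a difference, whereas error that differs by group can create, hide or reverse one.

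The listed primary outcomes are three questionnaire scales and a knowledge test, all answered by the woman. The two secondary outcomes are the only listed ones that could rest on records, so the study loses its one chance of evidence that does not depend on the participant's answers.

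A second issue affects diabetes control. The plan does not define it and does not say how a woman with no postpartum glucose test is classified.

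**Working it through.** **Reading the sections together.** The plan offers no figure to reproduce here. Its minimum of 30 women per group is stated without an endpoint, effect size or event rate, and is not tied to these outcomes. The check is therefore first a reading of the text:

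1. Secondary outcomes names a researcher-made form for each outcome and nothing else.
2. Data collection puts all data into interview questionnaires.
3. No section names a delivery, neonatal or laboratory record, lists the complications that count, defines diabetes control or describes blinding.
4. Validity and reliability reports Cronbach's alpha for the HPLP-II, CES-D and SF-36 only, and gives no validity or reliability information for either form.
5. Data analysis contains no check on reporting or misclassification. It also calls the third assessment the postpartum 6th month, while the other sections say 6th week, so the recall interval needs reconciling.

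Taken together, the stated method for both outcomes is maternal report.

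**How much could it matter?** Every rate below is an assumption. Only the group sizes come from the documents: 46 intervention and 42 control at the first assessment (design section). Assume that all 88 contribute an outcome and that no woman reports an event that did not occur.

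Observed rate = true rate × proportion of events reported. With a true rate of 20% in both groups:

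- 0.20 × 0.90 = 0.18 and 0.20 × 0.70 = 0.14, a spurious gap of 4 points. In a group of 46 that is 0.04 × 46 = 1.8, or about two women.
- At true rates of 10% and 30% the gap is 0.10 × 0.20 = 2 points and 0.30 × 0.20 = 6 points.
- With 95% against 60% reported, the gap is 0.35 × the true rate: 3.5, 7 and 10.5 points at 10%, 20% and 30%.

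False-positive rate of the uncorrected chi-square test at two-sided 0.05, with no true difference: sum Bin(x; 46, p₁) × Bin(y; 42, p₂) over all pairs (x, y) with |z| > 1.96, where z = (x/46 − y/42) / √[p̄(1 − p̄)(1/46 + 1/42)] and p̄ = (x + y)/88. Here p₁ and p₂ are the observed rates.

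| True rate, both groups | 90% reported in both | 70% intervention, 90% control | 90% intervention, 70% control |
|---|---|---|---|
| 20% | 4.9% | 7.8% | 7.5% |
| 30% | 4.9% | 10.0% | 9.9% |
| 40% | 4.8% | 11.9% | 12.4% |
| 50% | 4.8% | 15.4% | 16.0% |

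Most of the rejections in the third column favour the programme (7.15 of 7.79 percentage points at a true rate of 20%). Most of those in the fourth column go against it.

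With a real effect, say 15% intervention against 40% control, power is 76% under complete reporting. If 95% of events are reported in the intervention group and 70% in control, the observed rates are 0.15 × 0.95 = 14.25% and 0.40 × 0.70 = 28%, and power falls to 36%. With the proportions reversed, the rates are 0.15 × 0.70 = 10.5% and 0.40 × 0.95 = 38%, and power rises to 88%.

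**The case against.** The strongest reply is that the forms are not reproduced. A form completed at interview can still carry figures from a discharge summary or a result sheet that the mother brings. A reader might infer that no record was ever consulted, but the documents do not show that. They show only that no record is named and that interview is given as the method for all data. If records were used, saying so would largely settle the source question.

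A reader might also infer that reporting bias occurred, or that it favours the programme. Neither is supported. The direction is unknown, and the taught topics are the mother's own care, blood glucose and breastfeeding. Neonatal complications are not listed as a topic, so the awareness argument is weaker for H4 than for glucose results. Birth weight or admission to a neonatal unit is also memorable, and a reporting gap of 20 to 35 points between groups may be too large for such items.

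A third inference would be that untested women were counted as controlled. No coding rule is given either way. Diabetes control could even mean attending a check, for which interview is a usual source.

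Finally, these are secondary outcomes. That limits the weight of the point, although H4 is one of four formal hypotheses. All these objections limit how far the point goes, but none supplies a source for the outcomes other than the interview.

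**Conclusion.** The point holds in a limited form. As written, the neonatal outcomes behind H4 and postpartum diabetes control rest on maternal report to an interviewer for whom no blinding is described. Differential reporting between the educated and control groups can therefore enter both comparisons, in an unknown direction.

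The documents give no basis for a size. In the main illustration (true rate 20%, reporting 90% against 70%), the false-positive rate rises from about 4.9% to 7.5-7.8%, which is modest. Larger distortions need higher assumed event rates or wider reporting gaps. These calculations concern the neonatal chi-square test; the Fisher test for diabetes control was not computed. The finding itself rests only on the wording of Data collection and Secondary outcomes, and not on any assumed rate. It is a worthwhile and cheap improvement, and does not show that the results are wrong.

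**What to change.** In the Secondary outcomes section:

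- Name the delivery or neonatal hospital record as the source for each neonatal item: birth weight, gestational age at birth, diagnosed complication and neonatal unit admission. Use maternal report only for births elsewhere, and flag it in the data.
- Split diabetes control into (a) whether a postpartum glucose test was done by week 6, with all women as the denominator, and (b) the laboratory result among those tested. Untested women then cannot count as controlled. Read (b) beside (a), because the education may affect who is tested.

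The existing data collector can do the look-ups, 46 + 42 = 88 women, because the items are objective record entries. This would not be blinded extraction, since that person collected data in both groups, and the plan should not describe it as blinded. The cost is a modest extra workload. Some records from other hospitals may be unavailable, so a few items would remain maternal report.

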## **Desing**

The study was designed and conducted as a two group quasi-experimental study. Intervention group (n=46) and control group (n=42) were administered the data collecting tools in the first assessment. After first assessment, the intervention group were included in the educational program. Data collecting tools were re-administered four weeks after to the intervention group only. Than data collecting tools were re-administered to the both groups in the postpartum 6th week.

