### **Validity and reliability**

Women with GDM in the intervention and control group were divided into groups by randomization method. Women with GDM who were followed up in the perinatology clinic were divided into groups by means of a lottery method. In the clinic, women in

the same room were not taken to different groups to avoid problems among GDM women.

In this study reliability of the instruments was measured with Cronbach's alpha. The Cronbach's alpha value of the HPLP II was 0.90; the CES-D was 0.85 and the SF-36 was 0.85.

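### Some assignments could be known in advance, the design label is inconsistent, and the only post-program group comparison of the three scales ignores the first-assessment score

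*Combined protocol and SAP*

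**What the plan says.** The allocation procedure is described under Secondary outcomes. Patients were "assigned to groups through randomization (drawing lots by the clinic nurse". If several eligible women were present, a lottery decided. If only one was present, "it was determined which group to take with the lot but the next patient was taken directly to the opposite group". A further rule covers shared rooms: "When two patients were in the same room, they were taken into the same group in order not to have any ethical problems". No concealment beyond the nurse's drawing of lots is described.

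The labels differ between sections:

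- Secondary outcomes: randomization, as quoted above.
- Validity and reliability: "Women with GDM in the intervention and control group were divided into groups by randomization method", and again "divided into groups by means of a lottery method". This section repeats the room rule but not the opposite-group rule.
- Design (spelled Desing in the document): "The study was designed and conducted as a two group quasi-experimental study".

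On measurement, the Design section says "Intervention group (n=46) and control group (n=42) were administered the data collecting tools in the first assessment". Of the second assessment it says "Data collecting tools were re-administered four weeks after to the intervention group only". Both groups were measured again only at the third assessment, after birth.

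The Data analysis section compares introductory characteristics between groups by chi-square and Mann-Whitney tests, and compares the first and the third assessments between groups by Mann-Whitney tests. It names no covariate, change-score or other adjusted analysis.

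**The concern.** A lot protects a comparison only while nobody can foresee its result. Under the opposite-group rule, anyone who knows the previous assignment and the rule knows the next one. The text says that the data collector checked the clinic daily for patients, and the Data collection section says that one person collected the data in both groups. Whoever found the next eligible woman could therefore have known where she would go, which leaves room for approach or consent to differ by group.

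Any resulting difference at the first assessment passes into the third-assessment comparison, because that test uses the third score alone. The second assessment has no control data, so this one test is the whole between-group evidence after the program for the three scales behind H1 to H3.

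The labels add to the problem. A reader who checks for bias under Validity and reliability finds a lottery and a room rule, and no mention that some women were placed without a lot.

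**Working it through.** **Inputs.** Group sizes 46 and 42, total 88 (Design section). The documents give no count of women by assignment route, no first-to-third correlation and no size of imbalance. The plan has no figure of its own on this point to reproduce.

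**1. How many women could have been placed by the opposite-group rule.** Read as pairs (one woman by lot, the next opposite), each complete pair puts one woman in each group. The number of pairs is at most min(46, 42) = 42. Rule-placed women therefore number 0 to 42, and 42/88 = 47.7%. This assumes that the 88 are all the women assigned.

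**2. What the baseline comparison can detect.** For one scale, in SD units:

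- SE = sqrt(1/46 + 1/42) = 0.2134.
- Imbalance detectable with 80% power, two-sided 5%: (1.960 + 0.842) × 0.2134 = 0.598 SD.
- Mann-Whitney test, normal data, 20,000 simulated trials: 15.0%, 27.2% and 44.1% power at 0.2, 0.3 and 0.4 SD; 79.4% at 0.62 SD.

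If all three scales shift by 0.3 SD, the chance that at least one is flagged is higher. With independent scales it is 1 − (1 − 0.272)³ = 61.4%; by simulation it is about 62%, falling to about 44% when the scales correlate at 0.7.

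**3. What a missed imbalance would do (illustration only).** Assume a first-score imbalance of 0.3 SD, no program effect, correlation r between first and third scores, and bias acting only through the first score. The third-score means then differ by r × 0.3 SD.

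| Assumed r | Carried shift (SD) | Shift / 0.2134 | Type I error, normal approximation | Mann-Whitney, simulated | ANCOVA, simulated |
|---|---|---|---|---|---|
| 0.3 | 0.09 | 0.42 | 7.1% | 6.6% | 4.8% |
| 0.5 | 0.15 | 0.70 | 10.8% | 10.3% | 4.9% |
| 0.7 | 0.21 | 0.98 | 16.6% | 15.9% | 4.9% |

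The normal approximation is P(Z > 1.96 − shift/SE) + P(Z < −1.96 − shift/SE). For r = 0.5 that is P(Z > 1.257) + P(Z < −2.663) = 0.104 + 0.004 = 0.108.

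**4. Precision.** Adjustment multiplies the SE by about sqrt(1 − r²): 0.954, 0.866 and 0.714 at r = 0.3, 0.5 and 0.7. This ignores the small cost of estimating the slope and of any imbalance. The adjusted analysis is therefore worth having even if the groups are balanced.

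**The case against.** Much of the case on the other side is sound.

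- **The allocation is not shown to be non-random.** On the paired reading it is a random block of two: each woman's chance of either group is still one half, and the weakness is that the second assignment is not concealed. A reader might infer fixed alternation after a single first lot, which would determine 87 of 88 assignments. Strict alternation of 88 women gives 44 and 44, however, not 46 and 42, and the text keeps a lottery for days with several eligible women. The documents do not support relabelling the method as alternation.
- **The range of 0 to 42 includes zero and is not firm.** The Sample section planned 50 per group, and the flowchart cannot be seen in the copy reviewed. If 50 and 50 had been assigned and the 12 women not among the 88 had all been placed by lot, 50 of the 88 could be rule-placed.
- **The baseline check is stronger than one scale suggests**, as step 2 shows. Even so, it detects and does not correct.
- **ANCOVA's advantage in the table is built in**, because the simulated bias acts only through the first score. Selection on motivation or other unmeasured factors would remain.
- **The room rule is disclosed, with its reason, in both sections.** Room clustering and any analysis by route depend on records that the documents do not mention.
- **The Design section already says quasi-experimental.** That is a fair disclosure, but it leaves the plan inconsistent with itself.

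None of this answers the remaining points: some assignments were predictable, no concealment of them is described, the labels disagree, and the comparison that matters is unadjusted.

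**Conclusion.** The point holds in a limited form and should be fixed. The textual facts are certain: the opposite-group rule makes some assignments knowable in advance, the three sections do not agree on the label, Validity and reliability omits the rule, and the third-assessment Mann-Whitney test is the only post-program between-group comparison of HPLP-II, CES-D and SF-36.

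The size of any bias is unknown. A reader might infer that enrolment was selective, that nearly half the women were placed by rule, or that the true false-positive rate is 10% to 16%. The documents show none of these. The first is a possibility only, the second is a ceiling under stated assumptions, and the third depends on an assumed 0.3 SD imbalance and assumed correlations.

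The case for changing the analysis does not need them. The first-assessment scores exist in both groups, and using them removes the part of any imbalance that those scores carry and usually narrows the interval.

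**What to change.** **Main change, Data analysis section.** Compare third-assessment HPLP-II, CES-D and SF-36 scores between groups by ANCOVA, with group as factor and the first-assessment score of the same scale or subscale as covariate. Use a rank-based version if the residuals are clearly non-normal. Report the adjusted difference with its confidence interval and keep the Mann-Whitney test as support. State two limits: adjustment does not remove selection on unmeasured factors, and the first score may have been taken after assignment. Say which came first.

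**Text changes.** Use one design label across the Design, Secondary outcomes, and Validity and reliability sections. Add the opposite-group rule to Validity and reliability, say that it made some assignments predictable, and say whether any concealment was used. Interpret H1 to H3 in that light.

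**Optional, only if assignment and room records exist.** Report counts by route, use room-clustered standard errors, and repeat the comparison without rule-placed women. The last could leave only 88 − 42 = 46 women, for example 25 and 21. The SE would then be sqrt(1/25 + 1/21) = 0.296, which is 0.296/0.2134 = 1.39 times as large, so it is a low-precision check.

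**Cost.** The main change is one further analysis of scores already collected in both groups. All 88 women are reported as having had the first assessment, so the covariate should cost few or no women beyond those already missing the third. The text changes cost a more cautious causal claim.

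### The opposite-group rule and the same-room rule conflict when the patient after a lone woman joins her room, and the likely resolution assigns her by room placement, not by lot

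*Combined protocol and SAP*

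**What the plan says.** Allocation is described under Secondary outcomes. The clinic nurse is said to draw lots, and the text then gives three working rules:

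- Several eligible women: "If there were more than one patient who met the inclusion criteria, it was determined which group to take with the lottery method".
- One woman alone in the clinic: "it was determined which group to take with the lot but the next patient was taken directly to the opposite group".
- Shared room: "When two patients were in the same room, they were taken into the same group in order not to have any ethical problems".

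No exception or order of precedence links the second and third rules. The Validity and reliability section again describes randomization by lottery and says that women in "the same room were not taken to different groups to avoid problems among GDM women". It does not mention the opposite-group rule. The design section, by contrast, calls the study quasi-experimental, with 46 women in the intervention group and 42 in the control group.

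On who knew what, the allocation text says "Data collector checked patients in the perinatology clinic daily", and the Data collection section says that one person collected the data in both groups. No section says who assigned rooms or on what basis.

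**The concern.** A lot protects a comparison because nothing about the woman can influence her group. Under the opposite-group rule alone, the second woman already has no draw, and her group is known in advance. The room rule adds something different. Once the lone woman's group is known, placing the next patient with her leads to one group and placing her elsewhere leads to the other. Anything that influences placement, including clinical state, could then be associated with group.

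The affected comparisons are the between-group ones in the Data analysis section: questionnaire scores at the third assessment, neonatal characteristics and postpartum diabetes control. That section has no adjustment, no variable for route of assignment and no sensitivity analysis. The questionnaires at least have a first assessment on which the groups can be compared. The neonatal outcomes behind H4 have no baseline value.

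**Working it through.** The plan states no figure on this point, so the check is of the rules themselves.

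**Step 1. Do the rules conflict?** Let A be the lone woman, allocated by lot, and B the next patient. Both rules are taken from the Secondary outcomes section.

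| A's lot | B's room | Opposite-group rule puts B in | Same-room rule puts B in | Conflict |
|---|---|---|---|---|
| Intervention | A's room | Control | Intervention | Yes |
| Control | A's room | Intervention | Control | Yes |
| Intervention | Another room | Control | Not applicable | No |
| Control | Another room | Intervention | Not applicable | No |

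The rules disagree in 2 of 2 cases when the room is shared and in 0 of 2 otherwise. The conflict needs A still to be in the clinic when B joins her room.

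**Step 2. Which rule prevailed?** The room sentence directly follows the opposite-group sentence and carries an ethical reason. The Validity and reliability section repeats it without exception. The likely reading is that the room rule overrode the other, but neither section says so.

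**Step 3. What decides B's group?** Let q be the share of such second patients placed in A's room. If the room rule prevails:

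P(B in A's group) = q, and P(B in the opposite group) = 1 − q.

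The documents do not give q. Over an assumed range of q = 0, 0.1, 0.25, 0.5 and 1, the probability that B is in A's group is 0, 0.1, 0.25, 0.5 and 1. Room placement settles it. If the opposite-group rule prevailed instead, B's group is fixed by A's lot. If precedence was decided case by case, whoever applied the rules decided it. None of the three possibilities includes a lot for B.

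**Step 4. Are the observations independent?** Roommates allocated together share one assignment, whereas the Mann-Whitney, chi-square and Fisher tests treat each woman as independent. For pairs, the variance inflation is 1 + (2 − 1) × ICC. The ICC is not given. At assumed values of 0.05, 0.10 and 0.20 the inflation is 1.05, 1.10 and 1.20 if every woman were in such a pair, and less if only some were.

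**The case against.** The strongest reply is that the text supplies its own precedence: a lot, then alternation, with the room rule as an overriding exception. This largely stands. A reader might infer that the plan could not be carried out at all. The documents do not support that, because the conflict is confined to one situation and the Validity and reliability section points to how it was settled. That settlement does not restore a lot, however.

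A second reply is that the room sentence may mean only one joint lot for two women present together, with nothing said about later arrivals. That reading is possible. But if B then went to the opposite group while sharing A's room, roommates would have been split, which the Validity and reliability section says did not happen.

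A reader might also infer that staff chose the groups, since one person both screened daily and collected all the data. The documents do not show this. The clinic nurse drew the lots, nobody is named as assigning rooms, and there is no sign that placement was steered or followed prognosis. The rules left room for it, and no more than that can be said.

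Finally, a reader might want a figure for the bias, by assuming a number of steered women and a difference in their prognosis. Both inputs would be invented, so the result would say nothing about this study. The between-group comparison of introductory information and first assessments is a partial check on measured imbalance, but not on unmeasured imbalance.

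It also stands that the loss of chance is wider than the conflict, because every opposite-group assignment lacked a draw. The remedy therefore has to cover that route too.

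**Conclusion.** The concern holds in a limited form. The two rules contradict each other whenever the patient after a lone woman joins her room. If the room rule prevailed, as the Validity and reliability section suggests, her group followed from room placement with no lot, in a study that two sections describe as randomized and the design section calls quasi-experimental. The contradiction itself rests only on the current wording. That the room rule prevailed is an inference. The frequency of such assignments, the direction of any bias and its size cannot be derived from the documents. The point merits a correction and a sensitivity analysis; it does not show that the results are biased.

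**What to change.** **Procedure (Secondary outcomes section), for any further enrolment.** Delete the opposite-group rule. Draw a lot for every eligible woman, with one joint lot only for women who are eligible in the same room at the same time. Do not let a later arrival's group be set by the room she is placed in; for example, do not enrol her while an enrolled woman is in that room. A single lot per room that later arrivals inherit would not be enough, because placement would still set their group.

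**Women already enrolled.** Leave the description of what was done. State which rule prevailed, who assigned rooms and whether they knew the current groups. Where records allow, classify each woman as: own or joint lot; opposite-group; joined an enrolled woman's room. Report the counts by group.

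**Data analysis section.** Repeat the third-assessment, neonatal and postpartum diabetes comparisons in women allocated by their own or a joint lot only, leaving out opposite-group and inherited assignments. Treat roommates allocated together as a cluster, for instance with a permutation test that reassigns groups by lot and not by woman.

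**If routes cannot be recovered.** Describe the allocation as quasi-randomized throughout, in line with the design section's label, and limit the conclusions accordingly.

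**Cost.** One recorded variable, one sensitivity analysis and some rewording. Group sizes may be slightly less equal and a few women would not be enrolled. The sensitivity set is smaller and less precise: if, as an extreme assumption, all 46 + 42 = 88 women had arrived as a lone woman followed by an opposite-group patient, 88 / 2 = 44 would remain.
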